14.0 Number of Subjects

14.1 *Indicate the total number of subjects to be enrolled and how this number was determined (e.g., sample size calculation [show], number of available subjects in a finite pool, number of tests funding award would allow):*

In the preliminary data, we observed effect sizes ranging from $\eta^2 = .027$ to $\eta^2 = .074$. Thus, we selected a medium effect size ($f = 0.25$) to inform sample size of the current study. A total of 112 participants will complete the study (56 participants per group), assuming a type 1 error rate of 0.01 to account for multiple comparisons, 95% statistical power, and pre- and post-measure correlation of 0.25, based on an ANOVA comparing the intervention at sessions 1 and 2.

We anticipate a 70% retention rate; thus, to achieve a final sample size of 112, we anticipate consenting 160 participants.

14.2 If this is a multi-site study, indicate the number of subjects to be enrolled at this site and the total to be enrolled from all sites:

NA

14.3 If applicable, indicate the number of potential subjects you expect to screen for enrollment, and the number of subjects you will need to complete the research procedures:

We cannot accurately estimate the total number of potential participants we expect to screen. However, as described above, we anticipate enrolling 160 participants in order to complete a total of 112 participants. Additionally, the first few participants enrolled in the study may be pilots.

14.4 If the study has more than one procedure, indicate the total number of subjects to undergo each procedure separately:

All participants will undergo all sessions unless they withdraw from the study.

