2.0 Objectives

2.1 *Describe the purpose, specific aims, or objectives of this study:*

The goal of the present study is to test reinforcer pathology via manipulation of the temporal window (i.e., shorten the temporal window with exposure to a scarcity narrative). Another goal of the present study is to evaluate whether a voice recording can enhance the effects of a previously published scarcity narrative, compared to exposure to the written narrative only.

2.2 State the hypotheses to be tested:

We hypothesize a Group (Scarcity vs. Control) x Time (baseline vs. post) interaction. Specifically, we expect that participants exposed to an active scarcity narrative will present a shorten temporal view, as measured by Delay Discounting (DD), and increase demand for alcohol compared to baseline, whereas the control group would not show any changes between baseline and post intervention measures.

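### Does the stated 95% power rest on an effect much larger than the medium one the protocol names, so that section 14.1 must be changed?

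*Combined protocol and SAP*

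**What the plan says.** Section 14.1 of the combined protocol and SAP starts from earlier data, with eta-squared values between .027 and .074. From these the investigators conclude: "we selected a medium effect size ($f = 0.25$) to inform sample size of the current study". The result is 112 completers, 56 in each arm. The error rate is set by "assuming a type 1 error rate of 0.01 to account for multiple comparisons", and the other inputs are given as "95% statistical power, and pre- and post-measure correlation of 0.25, based on an ANOVA comparing the intervention at sessions 1 and 2".

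Section 2.2 hypothesises a Group by Time interaction in which the active arm changes, "whereas the control group would not show any changes between baseline and post intervention measures". Section 5.2 plans a repeated measures ANOVA.

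Section 14.1 does not say whether the eta-squared values are partial, or which outcome or contrast they describe. It does not express f = 0.25 as a difference in change, and it gives power at one effect size only.

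**The concern.** Three features of section 14.1 invite suspicion.

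- **Size of the effect.** In the repeated-measures formula that yields 112, f is scaled to the SD of a single-session score. In a 2x2 interaction, f = 0.25 then corresponds to a difference in change of a full single-session SD. Since the control arm is expected not to move, the active arm must supply all of it. A reader who takes medium to mean half an SD would be misled.
- **Choice within the range.** f = 0.25 corresponds to eta-squared .059, above the midpoint of the cited range (.0505) and 2.2 times its lower end (.0588/.027). Power at the lower end is well below 95%.
- **Possible double counting.** If the cited values are partial eta-squared from an interaction test, they already reflect the pre/post correlation. Dividing by (1 − rho) would then use it twice.

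At stake is how a null result on discounting or demand would be read in a study meant to test a theory. A 5% chance of missing a real effect differs greatly from 40% or 80%.

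**Working it through.** **Inputs (section 14.1).** f = 0.25; N = 112 (56 per arm); alpha = 0.01, two-sided because the test is an F test on 1 df; rho = 0.25; two sessions, so m = 2; preliminary eta-squared .027 to .074. The contrast is the Group by Time interaction of section 2.2. Equal variances at both sessions and complete cases are assumed.

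**1. The plan's own figure.** For the within-between interaction, lambda = f² × N × m/(1 − rho), with df 1 and N − 2.

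- N = 112: lambda = 0.0625 × 112 × 2/0.75 = 18.67; power 0.953.
- N = 110: lambda = 0.0625 × 110 × 2/0.75 = 18.33; power 0.949.

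So 112 is the smallest even N that reaches 95%. The enrolment figure also holds: 112/0.70 = 160.

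**2. What f = 0.25 means here.** The difference in change is 4f = 4 × 0.25 = 1.0 single-session SD. The SD of change is sqrt(2 × (1 − 0.25)) = 1.225, so this is 1.0/1.225 = 0.82 SD of change. Check: the SE of the difference in change is sqrt(2 × 1.5/56) = 0.2315, and 1.0/0.2315 = 4.32 = sqrt(18.67). By comparison, a difference of 0.5 single-session SD has 33% power and one of 0.5 SD of change has 51%.

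**3. Power over the cited range on the protocol's formula.** Convert with f = sqrt(eta²/(1 − eta²)).

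| eta² | f | lambda | Power |
|---|---|---|---|
| .027 (lower end) | 0.167 | 8.29 | 60% |
| .039 | 0.201 | 12.12 | 80% |
| .0505 (midpoint) | 0.231 | 15.88 | 91% |
| .0588 (f = 0.25) | 0.250 | 18.67 | 95% |
| .074 (upper end) | 0.283 | 23.87 | 99% |

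For 95% power, N would be 246 at the lower end and 88 at the upper end.

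**4. The conditional reading.** Suppose instead that the cited values are partial eta-squared from the interaction test. Then lambda = f² × N, without the m/(1 − rho) factor:

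- .027: lambda 3.11, power 20%
- .0505: lambda 5.96, power 43%
- f = 0.25: lambda 7.00, power 51%
- .074: lambda 8.95, power 64%

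With N − 2 in place of N, each figure falls by about one percentage point or less. On this reading, 95% power at f = 0.25 would need N = 290.

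**The case for a change.** The strongest case for a change is that the formula behind 112 demands an interaction far larger than the cited range if that range is in partial eta-squared. A lambda of 18.67 on 110 error df is a partial eta-squared of 18.67/(18.67 + 110) = 0.145, about twice the largest cited value. The protocol also says that evidence on demand is sparse, so the lower end of the range cannot be dismissed for that outcome. And the remedy is only words: name the type of eta-squared and its contrast, give the detectable difference in SD units, and report power at the lower end.

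Part of this stands. The 1.0 single-session-SD translation is correct and informative, the 60% at .027 is correct, and a reader would be helped by both.

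The rest does not carry. Section 14.1 writes eta-squared, not partial eta-squared, and names no contrast, so double counting is possible but not shown. It is not true that power is 60% or lower at the cited effect sizes. On the protocol's formula that holds only at the lower end, and even on the partial reading the upper end gives about 64%. Whether the effect counts as medium depends on the scale: 0.25 is the conventional label for f, and the same effect is 0.82 in SDs of change. Choosing a value somewhat above the midpoint of a range is a planning judgement. On the f scale the range runs from 0.167 to 0.283 with midpoint (0.167 + 0.283)/2 = 0.225, so 0.25 is not far off.

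**Conclusion.** No change is needed. Sample size, power, alpha, correlation and test agree with one another: 112 completers give 95.3% power at f = 0.25, as stated, and that effect lies inside the range the protocol cites. Power over the range is 60% to 99% on the protocol's formula, and at least 80% from about eta-squared .039 upward. Lower power at the weakest effect in a planning range is an ordinary trade-off, and the protocol attaches its 95% to f = 0.25, not to the whole range.

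This rests on reading the cited values on the same scale as the chosen f. If they are partial eta-squared from the interaction test, power would be about 20% to 64%. The documents do not settle this, and the investigators can from their own preliminary data. Stating the type of eta-squared and the detectable difference would be good optional reporting. It would leave the sample size and the analysis as they are and would correct no figure shown to be wrong. Whoever interprets a null result can use the estimate and its confidence interval, which do not depend on the planning value.

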4.0 Study Endpoints

4.1 *Describe the primary and secondary **study** endpoints. See links below for discussion of study endpoints and how they may differ from study objectives. These are most common in clinical trials but are sometimes applicable to other types of biomedical research, as well as social, behavioral, or educational research. See link below for a discussion.*

https://docs.google.com/document/d/1Wocz7K7a0hCQJPPO_khh511SQQjhGDDGHzcOPRHR5Tw/edit?usp=sharing

Primary:

Change in Delay Discounting: Change in discounting rates will be compared within-subjects across sessions and between groups.

Change in Alcohol Demand: Change in alcohol demand will be compared within-subjects across sessions and between groups.

Alcohol craving: Change in alcohol craving will be compared within-subjects across sessions and between groups.

Subjective time perception: Change subjective time perception will be compared within-subjects across sessions and between groups.

4.2 *Describe any primary or secondary **safety** endpoints. These should be included for all studies that are greater than minimal risk. (Minimal risk: The probability and magnitude of harm or discomfort anticipated in the research that are not greater in and of themselves than those ordinarily encountered in daily life or during the performance of routine physical or psychological examinations or tests.):*

These procedures are not more than minimal risk.

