5.0 Study Design and Statistical Analysis Plan

5.1 *Describe the basic study design/approach (e.g., qualitative study using five focus groups of first year students to describe assimilation into the university community; randomized controlled trial of a behavioral change intervention to increase dietary intake of whole grains; pre- post-test evaluation of new pedagogical techniques to improve adult literacy):*

The study will use a within-between design. Adults with AUD will be randomly assigned to two groups (active or control), balanced by discounting rate and sex. All participants will provide measures for all assessments pre and post exposure to the scarcity (or control) narrative.

5.2 *Describe corresponding data analysis plan/approach (e.g., content analysis of focus group transcripts; descriptive analysis followed by linear regression modeling; nonparametric analysis of pre- and post-test measures):*

Demographic characteristics will be summarized using descriptive statistics. We will compare outcome measures using a repeated measures ANOVA with active vs. control narratives as explanatory variables. Outcomes of interest include delay discounting and alcohol demand.

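### The flat 0.01 in section 14.1 is tied to no stated family of tests and is not carried into section 5.2; Holm over the four primary endpoints would keep family-wise error at 5% or less and give more power.

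*Combined protocol and SAP*

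**What the plan says.** Section 14.1 sizes the trial at 112 completers, 56 per group, "assuming a type 1 error rate of 0.01 to account for multiple comparisons, 95% statistical power", with a "pre- and post-measure correlation of 0.25, based on an ANOVA comparing the intervention at sessions 1 and 2". The effect size is justified by preliminary data: "we observed effect sizes ranging from $\eta^2 = .027$ to $\eta^2 = .074", and so "we selected a medium effect size ($f = 0.25$) to inform sample size of the current study". The number of comparisons behind the 0.01 is not given.

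Section 5.2 is the analysis plan: "We will compare outcome measures using a repeated measures ANOVA with active vs. control narratives as explanatory variables". It names delay discounting and alcohol demand as outcomes of interest. It states no significance level, adjustment or testing order.

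Section 4.1 lists four endpoints as primary: discounting, demand, craving and subjective time perception. Craving is worded like the others: "Change in alcohol craving will be compared within-subjects across sessions and between groups".

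Section 2.2 predicts a Group x Time interaction in which participants given the active narrative "will present a shorten temporal view, as measured by Delay Discounting (DD), and increase demand for alcohol compared to baseline". It does not say whether success requires both results or only one.

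**The concern.** A level used for sizing binds nobody at analysis unless the analysis section repeats it. Here it does not, and the sections differ on how many outcomes are in play: four in 4.1, two in 5.2. The analyst could apply 0.01 to each test, or 0.05 to each test, or an adjustment chosen later, and could defend each from the text.

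Two things are at stake, one on each branch. At 0.01 per test over the four primaries, error is controlled, but a uniformly better rule with the usual 5% family-wise guarantee is passed over. At 0.05 per test, family-wise error over the four primaries is not controlled. The two branches are alternatives, and they concern different quantities: power for two predicted outcomes in the first, and error over four endpoints in the second.

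**Working it through.** **Inputs.** From section 14.1: N = 112 (56 per group), f = 0.25, pre-post correlation 0.25, per-test level 0.01, power 95%, preliminary η² from .027 to .074. From section 4.1: four primary endpoints. The documents give no correlation between endpoints, so 0 and 0.5 are assumed where one is needed.

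**1. The plan's own figure.** For the Group x Time interaction with two groups and two times, λ = f² × N × 2 / (1 − ρ) with 1 and N − 2 degrees of freedom.
- λ = 0.0625 × 112 × 2 / 0.75 = 18.67, giving power 95.3% at 0.01.
- The smallest equally split N that reaches 95% is 112, and 112 / 0.70 = 160. Both of the plan's figures reproduce.
- At the low preliminary value, f² = 0.027 / 0.973 = 0.0277 (f = 0.167) and λ = 8.29. Power per test is 60% at 0.01.

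**2. Power for the two predicted outcomes at flat 0.01, if independent.**
- f = 0.25: 0.953² = 0.909, about 91%.
- η² = .027: 0.602² = 0.363, about 36%.

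**3. Error at flat 0.01 over four endpoints.** At most 4 × 0.01 = 4%. If independent, 1 − 0.99⁴ = 3.9%.

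**4. Why Holm over four tests cannot lose to flat 0.01.** The thresholds for the ordered p-values are 0.05/4 = 0.0125, 0.05/3 = 0.0167, 0.05/2 = 0.025 and 0.05. All exceed 0.01. If a p-value is at most 0.01, so is every smaller one, and each passes its threshold, so Holm reaches and rejects it. Family-wise error stays at or below 5% whatever the correlation.

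**5. Size of the gain.** The table gives the chance that discounting and demand are both significant. It comes from 400,000 simulated trials per scenario with independent endpoints. Holm missed no flat-rule rejection.

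| Scenario | Flat 0.01 | Holm |
|---|---|---|
| Four tests, only these two move, f = 0.25 | 91% | 94% |
| Four tests, only these two move, η² = .027 | 36% | 45% |
| Four tests, all four move, f = 0.25 | 91% | 98% |
| Four tests, all four move, η² = .027 | 36% | 58% |
| Five tests, only these two move, f = 0.25 | 91% | 92% |
| Five tests, only these two move, η² = .027 | 36% | 40% |

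The five-test rows count money and alcohol discounting separately (section 8.3). Holm's first threshold is then 0.05/5 = 0.01, so it still rejects at least as much as the flat rule.

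**6. The other branch: 0.05 per test over four null endpoints.** If independent, 1 − 0.95⁴ = 18.5%. At correlation 0.5 it is about 16%. The upper bound is 4 × 0.05 = 20%.

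**The case against.** The strongest defence is that 0.01 is valid. The trial was sized at that level, each test keeps 95% power at the planned effect, and four-endpoint error is at most 4%. A rule stricter than needed is not an error. That stands, and it limits the point to an unstated family and an avoidable loss of power.

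The gain from Holm also depends on the family. With six or more tests Holm starts at 0.05/6 = 0.0083 or lower and can reject less than flat 0.01. However, the bound for flat 0.01 is then 6% or more, so the flat rule no longer guarantees 5%. This stands as a reason to name the family, since Holm cannot be applied without a count.

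Four stronger readings are tempting, and the documents do not support them:
- *The trial runs an 18.5% false-positive risk.* That figure needs independence, no effect on any of the four endpoints, and an analyst who sets section 14.1 aside.
- *0.01 fits no endpoint count.* Section 8.3 describes discounting of both money and alcohol. Counting both gives five primary tests, and 0.05/5 is 0.01. The plan does not state this derivation, but it cannot be ruled out.
- *The main claim needs both discounting and demand.* Section 2.2 predicts both but sets no success rule. If both were required, each could be tested at 0.05 with an error of at most 5% for the joint claim.
- *The 95% is overstated.* It is correct as power for one test. It lacks only a label saying so.

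**Conclusion.** The point holds as a gap in the decision rule with a better method available. The 0.01 is attached to no stated family and is absent from the analysis plan. For the four primaries in section 4.1, Holm at a family-wise 0.05 is uniformly more powerful than flat 0.01 and keeps the 5% guarantee.

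The gain is modest at the planned effect: 3 percentage points if only the two predicted outcomes move, and 7 if all four do. It is material at the lowest preliminary effect, at about 9 and 22 points. With five tests it shrinks to about 1 and 4 points. These figures assume 112 completers, the plan's pre-post correlation of 0.25 and independent endpoints. That Holm rejects at least as much as flat 0.01 for families of up to five tests needs no assumption about correlation. The error of 16% to 18.5% applies only if section 5.2 is run at 0.05 per test.

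**What to change.** Add to section 5.2:

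> The Group x Time tests of the four primary endpoints in 4.1 (one pre-named measure each for delay discounting, alcohol demand, craving and subjective time perception) are judged by the Holm procedure at a two-sided family-wise level of 0.05.

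Name the four measures there. This matters because section 8.3 lists two discounting commodities and two craving instruments. If money and alcohol discounting are both to be primary, state five tests instead. State also whether success requires both discounting and demand.

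In section 14.1, keep 0.01 as a conservative sample-size basis and label the 95% as power per endpoint. Add that the chance of discounting and demand both being significant at 0.01 is about 91% if they are independent.

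The cost is a few sentences, made before the data are analysed, with no new participants, data or procedures. Against flat 0.01, family-wise error over the four primaries rises from about 4% to at most 5%, and simple simultaneous confidence intervals are no longer available.

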15.0 Recruitment Methods

15.1 Describe when, where, and how you will recruit potential subjects:

Participants will be recruited from our REDCap data base. Previously screened participants who have agreed to be re-contacted for other studies will be contacted via email with an invitation to participate in the current study.

15.2 Describe the source of subjects (for example, clinic patients with specific conditions, students in the library, community members at a gathering, or members of a local gym):

Participants will be recruited from our REDCap database. Previously screened participants who have agreed to be re-contacted for other studies will be contacted via email with an invitation to participate in the current study.

15.3 Describe the methods that you will use to identify potential subjects:

We will check our current REDCap database, composed of participants that have screened in REDCap for other studies in our lab, and look for participants who: 1) have agreed to be re-contacted for future studies, and 2) reported alcohol use. We will then send out an email about the new study with a new REDCap screener link. All prospective participants will be required to fill out the new screener before enrolling for the current study to assure they meet all the inclusion criteria for the study.

15.4 Describe materials that you will be use to recruit subjects. Attach copies of these documents with this protocol in Protocol Management and be sure to include the IRB protocol number on each document.

- *For flyers, attach the final copy of printed flyers.*
- *For Virginia Tech News, Facebook postings and ads, newspaper ads, websites, MTurk/SONA/online survey systems, etc., attach the final wording and graphics to be used.*
- *For email recruitments, please include the subject line.*
- *For advertisements meant for audio broadcast, please submit the wording of the advertisement prior to taping (to avoid having to re-record with approved language) and submit the final recorded version for IRB review before use.*
- *Describe any compensation to subjects. Separate compensation into appropriate categories, such as: reimbursement for expenses, time and effort, and additional incentives for study participation. For each category, specify the amount (including any pro-rated amount), schedule, and method of payment.*

A template of the invitation email is attached.

Compensation. Participants will be compensated for each survey completed and will receive a study completion bonus if they complete both sessions. Compensation will be provided via online gift cards. Participants will be required to complete an online W-9 form in order to receive the payment.

Session 1: \$15

Session 2: \$20

Study completion bonus: \$5

16.0 Withdrawal of Subjects

16.1 Describe circumstances under which you anticipate subjects could be withdrawn from the research without their consent:

Participants may be withdrawn from the research without their consent if they become ineligible based on inclusion/exclusion criteria or learning of a contraindication for continuing, or if they demonstrate inconsistent responding during baseline assessment.

16.2 If applicable, describe any procedures for orderly termination (e.g., discontinuation of a study drug or debriefing after a behavioral intervention):

If a participant is withdrawn from the study, he or she will be informed that we have collected all the data required from their participation. If a participant is withdrawn or voluntarily discontinue, their compensation for the study will be pro-rated accordingly.

16.3 Describe procedures that you will follow when subjects withdraw from the research, including partial withdrawal from procedures with continued data collection (e.g., participant declines to continue with regular blood draws, but continues with periodic behavioral questionnaires):

If a participant is withdrawn or discontinued, they will be withdrawn from the entire study.

